5.2 Exclusion Criteria

Subjects are excluded from the study if any of the following criteria apply:

1. Subject is a female who is breastfeeding, pregnant, or who is planning to become pregnant during the study.
2. Employee of the study center or RAPT.
3. Subject has any serious and/or uncontrolled medical condition (including cognitive impairment or signs/symptoms suspicious for a serious disease) or laboratory abnormality that would place subject's safety at risk or interfere with study participation, as judged by the Investigator including but not limited to the following:
 - Moderate-to-severe asthma that is uncontrolled
 - Subjects with uncontrolled diabetes (hemoglobin A1c [HbA1c] $\geq 9\%$)
 - Stage III or IV cardiac failure according to the New York Heart Association classification
 - Severe renal conditions (e.g., subjects on dialysis)
 - Active autoimmune disease (e.g., systemic lupus erythematosus, rheumatoid arthritis, inflammatory bowel disease)
4. Subject has had a major surgery in the past 8 weeks or has a major, elective surgery planned during the study.
5. Subject has any clinically significant medical condition or physical/laboratory/ECG (e.g., acute myocardial infarction, clinically significant arrhythmia, or indications of serious underlying heart disease)/vital signs abnormality that would, in the opinion of the Investigator, be indicative of an underlying medical condition, put the subject at undue risk, and/or interfere with interpretation of study results.
6. Any of the following specific laboratory findings:
 - Alanine aminotransferase (ALT) $>2.5\times$ upper limit of normal (ULN)
 - Estimated glomerular filtration rate (eGFR) <60 mL/min/1.73m² (Modification of Diet in Renal Disease [MDRD] equation)
Note: For subjects between the ages of 50 to 75 years old with an eGFR lower than 60 mL/min/1.73 m² but potentially within normal range for the subject's age, please contact the Medical Monitor to discuss the subject's eligibility
 - Platelet count $<75,000$ cells/mm³
 - Hemoglobin <10 g/dL
 - Absolute lymphocyte count <800 cells per mm³
 - Absolute neutrophil count <1500 cells per mm³
7. Subject has a history of drug and/or alcohol abuse in the last 12 months.
8. Subject has a history of skin disease or presence of skin condition that, in the opinion of the Investigator, would interfere with the study assessments.
Note: Fungal infection of nail beds is allowed.

9. Subject has any state of immunodeficiency due to primary or secondary immunodeficiency syndromes, organ transplant (except corneal transplant), previous opportunistic infections, or any other state of immunodeficiency, as judged by the Investigator.
10. Subject has used tanning beds or phototherapy (narrowband ultraviolet B [NBUVB], UV-B, ultraviolet A1 [UVA1], or psoralen-UV-A [PUVA]) within 4 weeks prior to the Baseline visit.
11. Subject has received treatment with systemic immunosuppressive/immunomodulating drugs (e.g., methotrexate, cyclosporine A, mycophenolic acid, or azathioprine), immunoglobulins, blood products and/or systemic corticosteroids (e.g., oral, intravenous, intraarticular, rectal) within 4 weeks prior to the Baseline visit.
Note: Intranasal corticosteroids and inhaled corticosteroids are allowed. Eye and ear drops containing corticosteroids are also allowed.
12. Subject has used any topical medicated treatment that could affect AD within 2 weeks prior to the Baseline visit, including, but not limited to, topical corticosteroids, topical PDE4 inhibitor (e.g., crisaborole), topical calcineurin inhibitors, topical JAK inhibitors (e.g., ruxolitinib), tars, topical antimicrobials, and medical devices.
13. Subject has used medicated emollients (regulated as a medical device) within 7 days prior to the Baseline visit.
14. Subject has received RPT193 in the past.
15. Subject has received an investigational oral, systemic agent within 8 weeks or 5 half-lives (whichever is longer) prior to the Baseline visit.
16. Subject has received any marketed (other than dupilumab as described in exclusion criterion 17) or investigational biological therapeutic within 16 weeks or 5 half-lives (whichever is longer) prior to the Baseline visit.
17. Subject has used dupilumab within 12 weeks or tralokinumab within 16 weeks prior to the Baseline visit OR has received dupilumab or tralokinumab at any time in the past and was considered to have no clinical response within 4 months of initiating dupilumab or tralokinumab treatment.
Note: Lack of clinical response to dupilumab or tralokinumab may be defined by subject history alone.
18. Subject has used a systemic JAK inhibitor (e.g., tofacitinib, baricitinib, abrocitinib, upadacitinib) within 8 weeks prior to the Baseline visit OR has used a systemic JAK inhibitor at any time in the past and was considered to have no clinical response within 4 months of initiating JAK inhibitor treatment.
Note: Lack of clinical response to a JAK inhibitor may be defined by subject history alone
19. Subject is receiving a concomitant medication for condition(s) other than AD that require a change in dosing regimen within 7 days prior to the Baseline (Day 1) visit.
20. Subject has used a cell-depleting agent, including but not limited to rituximab within 6 months prior to the Baseline visit, or until lymphocyte counts return to normal, whichever is longer.

21. Subject has begun an allergen-specific immunotherapy regimen or had a clinically relevant change to their immunotherapy within 4 weeks prior to the Baseline visit.
22. Subject has used topical products containing urea within 1 week prior to the Baseline visit.
23. Subject has used systemic antibiotics, antivirals, antiparasitics, antiprotozoals, or antifungals within 2 weeks or topical antibiotics within 1 week prior to the Baseline visit.
24. Subject has received a live or live-attenuated vaccine within 4 weeks prior to the Baseline visit or plans to receive a live or live-attenuated vaccine during the study and up to 4 weeks after the last study drug administration.
25. Subject has a history of a clinically significant systemic infection or serious skin infection requiring parenteral antibiotic treatment within 4 weeks prior to the Baseline visit, or oral therapy within 2 weeks prior to the Baseline visit.
26. Subject has a known active bacterial, viral, fungal, helminth, or mycobacterial, or any other infection at the Baseline visit (non-complicated recurrent muco-cutaneous infections such as cold sores, tinea pedis, or disto-lateral mild to moderate onychomycosis are not considered exclusionary).
Note: Subjects for whom infections have resolved and otherwise meet eligibility criteria may be rescreened up to once.
27. Active infection with severe acute respiratory syndrome coronavirus 2 (SARS-CoV-2) virus.
28. Subject has a diagnosis of, is suspected of having, or is at high risk for an endoparasitic infection unless clinical and laboratory assessment have ruled out active endoparasitosis prior to the Baseline visit.
29. Subject has a history of cancer or lymphoproliferative disease within 5 years prior to the Baseline visit. Subjects with treated and completely resolved cutaneous basal cell carcinoma and/or cutaneous squamous cell carcinoma in situ and/or cervical cancer in situ can be considered, as judged by the Investigator.
30. Subject has a positive tuberculosis (TB) infection test at screening. Subject will be evaluated for latent TB infection with a purified protein derivative (PPD) test, a QuantiFERON-TB Gold test, or a T-spot test. Subjects who demonstrate evidence of latent TB infection (either PPD \geq 5 mm of induration or positive QuantiFERON-TB Gold test, irrespective of bacilli Calmette-Guérin vaccination status) will not be allowed to participate in the study.
31. Subject has a positive screen for hepatitis B surface antigen (HbsAg), hepatitis C (HCV) antibodies, or human immunodeficiency virus (HIV) antibodies. For HbsAg or HCV antibody positive screening, subjects may be enrolled if reflex testing (e.g., HBV-DNA or HCV-RNA) is negative and indicative that there is no active infection.
32. Subject has a known hypersensitivity to RPT193 or its excipients.
33. Subject is not willing to minimize natural and artificial sunlight exposure during the study. Use of sunscreen products and protective apparel are recommended when sun exposure cannot be avoided.
34. Subject is not willing to maintain their baseline skin care regimen (e.g., bathing) or use of herbals and/or supplements through the duration of the study.

35. Subject who is still participating in a clinical trial or who has participated in a clinical trial within 1 month prior to the Screening visit.

Note: Please also refer to Exclusion Criteria 15 and 16 regarding those who participated in an investigational clinical trial.

5.3 Lifestyle Considerations

5.3.1 Meals and Dietary Restrictions

RPT193 has been demonstrated to have similar PK and tolerability properties whether taken in a fasted or fed state. Thus, no restrictions related to food and ingestion of investigational product have been put in place. Investigational product should be taken with approximately 240 mL (8 ounces) of water. Subjects may discuss the pros and cons of taking the investigational product with food with the Investigator of their site.

5.3.2 Activity

Subjects should refrain from strenuous exercise or weightlifting within 96 hours (4 days) prior to screening and 48 hours prior to each subsequent visit as this could result in abnormal clinical laboratory values.

Subjects should try to limit exposure to the sun for the duration of the trial, but the use of sunscreen products and protective apparel are permitted when sun exposure cannot be avoided.

5.4 Screen Failures

Screen failures are defined as individuals who consent to participate in the clinical trial but are not subsequently randomly assigned to the study treatment. A minimal set of screen failure information is required to ensure transparent reporting of screen failure subjects, to meet the Consolidated Standards of Reporting Trials (CONSORT) publishing requirements, and to respond to queries from regulatory authorities. Minimal information includes demography, screen failure details, eligibility criteria, and any SAEs.

Subjects may be rescreened once provided the disqualifying reason is considered transient and is not related to disease activity status (i.e., vIGA, BSA, or EASI), if deemed acceptable by the Investigator. The Investigator may consult with the Medical Monitor on rescreening decisions if needed. Rescreened subjects should be assigned a different identification number than the initial screening. All procedures planned at the Screening visit, including signature of a new consent form, will be performed.

5.5 Replacement of Subjects

The study assumes a drop-out rate of 10% with a goal of enrolling approximately 265 subjects and approximately 240 subjects completing the study. Thus, no replacement of subjects is anticipated.

6.0 STUDY TREATMENT

Study treatment is defined as any investigational treatment(s), marketed product(s), placebo, or medical device(s) intended to be administered to a subject according to the study protocol.

The study consists of a screening period up to 35 days, a 112-day treatment period, and a 56-day follow-up period. Thus, the maximum duration of the study for an individual subject is 205 days (29 weeks). The study is anticipated to enroll approximately 265 subjects with 240 subjects completing the study (assuming a 10% drop out rate). The enrollment period is predicted to be 52 weeks. Thus, the duration of the study from initiation of Screening to the last Follow-up visit for the last subject enrolled is anticipated to be 81 weeks.

6.1 Study Treatment(s) Administered

RPT193-02 will consist of daily administration of 50, 200, or 400 mg of RPT193 or placebo for 16 weeks (112 consecutive days). The study drugs will be administered orally at approximately the same time of the day. On study days where PK samples are to be collected, the subject will administer the study drug at the study center, following the PK sample collection. The date and time of study drug administration will be collected daily via an electronic Diary (e-Diary) provided to the subject whether study drug is taken on- or off-site. The subject will be instructed to take the study drug at approximately the same time of the day when taken off-site. The subject will complete an e-Diary to document the time of each dose taken when off-site. Also, in the event of an adverse event of the gastrointestinal system organ class, the subject may be asked to indicate the timing of taking product in relation to food intake.

Further details regarding the study treatments can be found in [Table 2](#).

Table 2 Study Treatment Details

	Study Treatments	
Product name	RPT193	Placebo
Dosage form	Tablet	Tablet
Route of administration	Oral	Oral
Source of procurement of active substance	██████████ ██████████	Not applicable
Manufacturer	██████ ██████████	██████ ██████████

The contents of the label will be in accordance with all applicable regulatory requirements. Details on study drug preparation by ████████ can be found in the Manufacturing Batch Record. The active medication will be provided by the Sponsor.

6.2 Preparation/Handling/Storage/Accountability

1. The Investigator or designee must confirm appropriate temperature conditions have been maintained during transit for all study treatment received and any discrepancies are reported and resolved before use of the study drug.
2. Only subjects enrolled in the study may receive study drug and only authorized study center staff may supply or administer study drug. All study drugs must be stored in a secure, environmentally controlled, and monitored (manual or automated) area in accordance with the labeled storage conditions with access limited to the Investigator and authorized study center staff.
3. The study drug will be dispensed by the study site to the subject at the visits specified in [Table 1](#).
4. Subjects are to return all study drug to the study site. The RPT193 tablets will be counted upon return, and the counts will be recorded in the source documents and electronic case report form (eCRF).
5. Each subject will be instructed on the importance of returning the study drug at the next visit and on taking the product as prescribed. If a subject does not return study drug, he or she will be instructed to return it as soon as possible.
6. The Investigator, institution, or the head of the medical institution (where applicable) is responsible for study drug accountability reconciliation, and record maintenance (i.e., receipt, reconciliation, and final disposition records).
7. The Investigator, a member of the study center staff, or a hospital pharmacist must maintain an adequate record of the receipt and distribution of all study drug using the Drug Accountability Form, as per International Council for Harmonisation of Technical Requirements for Pharmaceuticals for Human Use (ICH) Good Clinical Practice (GCP). These forms must be available for inspection at any time by the Sponsor, its designees, or by regulatory agencies.
8. Further guidance and information for the final disposition of unused study drug are provided in the Study Reference Manual.

6.3 Measures to Minimize Bias: Randomization and Blinding

At the study site, each screened subject will be assigned an identifier number during screening that will be used on all documentation. The identifier number will contain the site number (YYYY) and the subject number (SSSS) and will be assigned at the Screening visit (e.g., YYYY-4001).

Randomization will occur prior to first dosing, at the Baseline (Day 1) visit. Approximately 265 subjects will be randomized 1:1:1:1 to one of 4 groups (3 dose levels of RPT193 or placebo). In total and accounting for a dropout rate of 10%, approximately 67 subjects are anticipated to complete the study in each group.

A randomization list will be generated using a validated software. The randomization list will be kept secured until the study blind is broken at the end of study.

The randomization list will be stratified based on region (North America vs. rest of world), baseline vIGA scores (vIGA of 3 vs. 4), and prior dupilumab or tralokinumab use (yes or no). (Note: Enrollment of subjects with a prior history of dupilumab or tralokinumab use will be capped at approximately 20%.) The list will be uploaded into an Interactive Web Response System (IWRS) and the Investigator or designee will be able to acquire a randomization number for eligible subjects by connecting to the IWRS.

Further guidance and information can be obtained in the Study Reference Manual.

This study will be double blind. At all times, treatment and randomization information will be kept confidential and will not be released to the Investigator, the study staff, the contract research organization (CRO), or the Sponsor study team until after the conclusion of the study. However, the laboratory where the PK samples will be analyzed will be provided with a copy of the randomization code since only samples of subjects who have received the active drug RPT193 will be analyzed.

The following controls will be employed to maintain the double-blind status of the study:

- The oral tablets containing active drug or placebo will be indistinguishable in appearance and taste.

Blinding codes should only be broken in emergency situations for reasons of subject safety. When the blind for a subject has been broken, the reason must be fully documented in the source document and eCRF. Whenever possible, the Investigator should contact the Sponsor or its designee before breaking the blind. If the blind is broken, the Investigator should promptly inform the Medical Monitor. Documentation of breaking the blind should be recorded with the date/time and reason why the blind was broken, and the names of the personnel involved.

The subject for whom the blind has been broken will be discontinued from the study and undergo the End-of-Treatment (ET)/Discontinuation procedures. In cases where there are ethical reasons to have the subject remain in the study, the Investigator must obtain specific approval from the Sponsor or its designee for the subject to continue in the study. The primary reason for discontinuation (the event or condition which led to the unblinding) will be recorded.

6.4 Study Treatment and e-Diary Compliance

Study treatment and Diary compliance will be monitored at the visits specified in the Schedule of Activities (SoA) ([Section 1.3](#)). Adherence to treatment will be assessed by direct questioning and by maintaining adequate study drug dispensing and return records. Any deviation from the prescribed dosage regimen will be recorded in the source document. Adherence to Diary completion will be assessed by a review of compliance reports by the site monitors prior to each

site visit or contact. Subjects who are significantly noncompliant with e-Diary completion (i.e., missing >20% of Diary entries) will be counseled and could be discontinued from the study, at the discretion of the Investigator, following consultation with the Sponsor.

On visit days, the date and time of study drug administration and the number of units administered will be recorded. In addition, subjects will capture the date and time of dosing in a daily e-Diary when the study drug will be taken at the site or at home.

Subjects who are significantly noncompliant with treatment (i.e., missing >20% of doses) will be counseled and could be discontinued from the study, at the discretion of the Investigator, following consultation with the Sponsor. A subject will also be considered significantly noncompliant if he or she intentionally or repeatedly takes more than the prescribed amount of study drug in the same time frame, as judged by the Investigator.

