7.2 Subject Discontinuation/Withdrawal from the Study

Subjects have the right to withdraw from the study at any time for any reason without penalty. The Investigator also has the right to withdraw subjects from the study if he or she feels it is in the best interest of the subject or if he or she is uncooperative or noncompliant.

Should a subject decide to withdraw, all efforts will be made to complete and report the observations as thoroughly as possible, particularly the examinations outlined in the Early Termination /Discontinuation (ET/Discon) visit.

The Investigator or one of his or her staff members should contact the subject to determine as accurately as possible the primary reason for the withdrawal.

A complete final evaluation at the time of withdrawal should be made with an explanation of why the subject is withdrawing from the study. If the reason for removal of a subject is an AE or an abnormal laboratory test result, the principal specific event or test will be recorded.

If a participant withdraws from the study, he/she may request destruction of any samples taken and not tested, and the Investigator must document this in the site study records.

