7.2.1 Discontinuation

Subjects who discontinue the study after the first dose will be asked, if they agree, to come for a last assessment (ET/Discon visit). Subjects who are discontinued for safety reasons may be asked to come for additional follow-up visits, at the Investigator's discretion, after the ET/Discon visit to ensure appropriate medical care and AE follow-up.

Reasons for discontinuation include the following:

- The Investigator decides that the subject should be withdrawn for any of the following reasons, but not limited to: difficulties in obtaining blood samples, violation of the protocol, severe AEs or SAEs, or for any other reason relating to the subject's safety or integrity of the study data. If this decision is made because of a SAE, the study drug is to be discontinued in that subject immediately and appropriate measures are to be taken. The Investigator will notify the Sponsor immediately.
- The attending physician requests that the subject be withdrawn from the study.
- The subject, for any reason, requires treatment with another systemic therapeutic agent that has been demonstrated to be effective for treatment of the study indication (e.g., oral corticosteroids, dupilumab, tralokinumab oral calcineurin inhibitor, oral immunosuppressive). In this case, discontinuation from the study occurs immediately upon introduction of the new agent.
- The subject is lost to follow-up. In this case, a reasonable attempt to contact the subject and ascertain his or her status must be made, and these attempts must be documented.
- The subject becomes pregnant at any time during the study.
- A clinically significant change in a laboratory parameter occurs (See [Table 4](#)),
- Onset of an opportunistic infection during the study.
- Other: the subject may withdraw from the study for any other reason, including withdrawal of consent.

- The Sponsor or regulatory authorities, for any reason, stop the study. In this case, all subjects will be discontinued from the study. The Investigator will immediately, on discontinuance of the study by the Sponsor, in its entirety or at a clinical trial site, inform both the subjects and the Institutional Review Board/Research Ethics Board/Independent Ethics Committee (IRB/REB/IEC) of the discontinuance, provide them with the reasons for the discontinuance and advise them in writing of any potential risks to the health of subjects or other persons.

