9.4.2 Primary Efficacy Analysis

The primary efficacy endpoint is the percent change from baseline in EASI score at Week 16.

The primary estimand is defined as

- Population of interest: adult subjects with moderate-to-severe AD as defined by the inclusion/exclusion criteria
- Variable/endpoint of interest: percent change from baseline in EASI score at Week 16.
- Intercurrent event handling strategy:
 - Early termination of study treatment: subjects who discontinue from the study treatment prior to Week 16 will be analyzed by the treatment policy strategy, i.e., all data collected will be included in analysis.
 - Use of rescue medications: subjects who use rescue medication during the 16-week treatment period will be analyzed by the hypothetical strategy. All EASI scores collected after the start of rescue medication will be set to missing and imputed.
- Population-level summary measure: difference in mean percent change from baseline in EASI score between RPT193 and placebo.

The primary analysis will be performed in FAS. The primary efficacy endpoint will be analyzed with ANCOVA model. The model will include treatment group (each RPT193 dose vs. placebo), baseline vIGA scores, randomization stratification factors and study sites as factor, and baseline EASI score as a covariate. The least square (LS) mean and LS mean difference along with the 95% confidence interval (CI) and p-value will be reported.

The following sensitivity analysis will be planned for the primary estimand:

- In FAS, including only the observed data regardless of rescue medication uses and without missing data imputation.
- In PP analysis set, following the same model as described for the primary estimand.

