### A. Efficacy Assessments

#### 1. Eczema Area Severity Index (EASI)

The EASI is a clinician assessment that is collected at Screening/ Visit 1, Baseline/ Visit 2, Visit 3/ Week 2, Visit 4/ Week 4, Visit 5/ Week 8, Visit 6/ Week 12, Visit 7/ Week 16, Visit 8/ Week 18, Week 9/ Week 20 and Visit 10/ Week 24 using the e-Diary.

The EASI is a composite score ranging from 0 to 72 that takes into account the degree of erythema, induration/infiltration (papules), excoriation, and lichenification (each scored as =None, 1=Mild, 2=Moderate 3=Sever) for each of 4 body regions (head and neck, trunk, upper extremities and lower extremities), with adjustment for the percentage of BSA (assessed by the palmar method) involved for each body region ( 0= 0%, 1=1-9%, 2=10-29%, 3=30-29%, 4= 50-69%, 5=70-89%, 6=90-100%) and for the proportion of the body region to the whole body (.1 for head and neck, .3 for trunk, .2 for upper extremities and .4 for lower extremities)

The domain score will be calculated in the ADaM dataset when all assessments are completed. The following is the calculation for each body region:

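### Protocol 6.4 allows removal from the study for missed diary entries or doses alone, so an obtainable Week 16 EASI may go uncollected and be imputed from placebo

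*Protocol*

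**What the plan says.** - **Triggers and consequence.** Protocol 6.4 sets two thresholds, "missing >20% of Diary entries" and "missing >20% of doses". For each, the subject is counselled and then "could be discontinued from the study, at the discretion of the Investigator, following consultation with the Sponsor". The object is the study, not study treatment. Protocol 7.2 separately lets the investigator withdraw a subject from the study "if he or she is uncooperative or noncompliant", and 7.2.1 lists protocol violation and data integrity among the reasons for discontinuation.
- **What follows removal.** Protocol 7.2.1 provides one ET/Discon assessment, if the subject agrees. Further visits are mentioned only for subjects discontinued for safety reasons. The schedule of activities (1.3, footnote j) ends the e-Diary at that visit.
- **Primary endpoint.** "The primary efficacy endpoint is the percent change from baseline in EASI score at Week 16" (Protocol 9.4.2). SAP VI.A.1 states "The EASI is a clinician assessment", made at scheduled visits; SAP VI.A.2 describes vIGA in the same way.
- **Estimand and analysis.** Under Protocol 9.4.2, subjects who stop study treatment before Week 16 "will be analyzed by the treatment policy strategy, i.e., all data collected will be included in analysis". SAP II.A keeps that strategy up to the start of rescue. The full analysis set is everyone randomised (SAP IV.H.1). Missing Week 16 values in every arm are imputed from placebo data (SAP IV.D.2, control-based multiple imputation).
- **How the SAP treats non-compliance.** Poor compliance with study treatment is a possible reason for exclusion from the per-protocol set (SAP IV.H.3); diary non-compliance is not listed. A weekly PP-NRS score needs three daily entries (SAP IV.C).

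**The concern.** A treatment-policy strategy needs outcome data from subjects who depart from their assigned regimen. A subject who forgets diary entries or skips doses may still be taking drug and may be willing to attend, and a clinician can rate EASI and vIGA without that subject's daily home entries. Protocol 6.4 nevertheless permits the sponsor and investigator to end that subject's participation.

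If this happens well before Week 16, a score that could have been measured becomes one modelled on placebo. The missing data then arise from a discretionary decision made after randomisation, with no criterion beyond the 20% threshold, so practice may differ between sites. The same removal ends the diary, turning incomplete PP-NRS data (a key secondary endpoint) into none. At stake are avoidable missing primary data and an effect estimate that leans more on the imputation model than it needs to.

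**Working it through.** **1. The plan's own numbers.** Protocol 9.2 and SAP III.C give 60 evaluable subjects per group and 10% drop-out. 60 / 0.90 = 66.7, rounded up to 67 per group; 4 × 67 = 268. This is the SAP total and is close to the protocol's approximate 265. Expected completers are 67 × 0.90 = 60.3 per group. The 60 itself cannot be checked because the effect size, SD and power are redacted.

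**2. How strict the diary threshold is.** Protocol 6.4 gives no base. On an assumed 112 treatment days, 0.20 × 112 = 22.4, so 23 missed entries suffice. Under SAP IV.C a subject may miss 4 of 7 entries (57%) in a week and still have an analysable PP-NRS score. The removal threshold is therefore far tighter than the analysis needs.

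**3. When a removal costs the Week 16 score.** The SAP's Week 16 window is Days 99 to 119, so an ET visit in that range supplies the value. Removal after Week 16 costs no primary data, only follow-up data. The loss applies to subjects whose last visit falls before Day 99.

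**4. Effect on the estimate.** Let r be the fraction of an active arm removed, δ the true effect in the rest, and kδ the true effect in those removed. Take imputation to give the removed subjects no benefit.

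- True effect over all randomised = δ(1 − r + rk)
- Estimated effect = δ(1 − r)
- Ratio = (1 − r) / (1 − r + rk)

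With r = 0.05 (assumed; the documents give no rate):

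| True benefit in removed subjects | Ratio | Estimate is |
|---|---|---|
| k = 1 (average benefit) | 0.95 / 1.000 = 0.950 | 5.0% too small |
| k = 0.5 | 0.95 / 0.975 = 0.974 | 2.6% too small |
| k = 0 (none) | 0.95 / 0.950 = 1.000 | unbiased |
| k = −0.5 (worse than placebo) | 0.95 / 0.925 = 1.027 | 2.7% too large |

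At k = 1 the shrinkage equals r, so removal of 2% or 10% gives 2% or 10%. Zero imputed benefit is the extreme case: the example code in SAP Appendix II regresses Week 16 on the subject's own earlier scores, so some earlier benefit would carry forward.

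**5. Power in the planned analysis set, as a bound.** Assume that 60 per group gives 80% power. The standardised effect is then (1.960 + 0.842) × √(2/60) = 0.511. Analyse all 67 per group with no effect in any drop-out fraction t: power = Φ(0.511 × (1 − t) × √(67/2) − 1.960). With t = 0.10 this is 75.9%; with t = 0.15 (five further points removed) it is 71.1%. If design power is 90%, the figures are 86.9% and 82.9%. The five extra points and the complete loss of effect are both assumptions.

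**The case against.** The best defence is that the clause is permissive. Removal comes after counselling and consultation, nothing in the documents suggests that it would be frequent, and the 10% drop-out allowance is not broken down by cause, so it may already cover these withdrawals. The diary also matters: it records rescue use (Protocol 6.6.4), which decides which EASI scores are set to missing, and it is the source of PP-NRS. Finally, the lack of follow-up after any discontinuation is the more general cause of missing Week 16 data. It also applies to the required withdrawal for topical therapy before Day 57 (6.6.4) and to default discontinuation after unblinding (6.3).

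Most of this stands as a limit on size. It does not justify the clause. Removing a subject also ends the recording of rescue and itch, so it cannot cure a poor diary. The other withdrawal routes rest on different reasons; this one needs none beyond missed entries or doses.

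A reader might infer more than the documents support:

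- *That scores are discarded.* They are not. The subject stays in the full analysis set and earlier scores are used; what is lost is a score not yet collected.
- *That every removal costs a Week 16 score.* Step 3 shows otherwise.
- *That 6.4 contradicts 9.4.2.* Section 9.4.2 promises to use the data that are collected. Section 6.4 reduces what is collected; it does not breach that promise.
- *That 5% removal cuts 60 evaluable subjects to 57 and an assumed 80% power to 78%.* That describes a completers analysis, not the planned analysis of all randomised subjects with imputation.

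**Conclusion.** The point holds as a design weakness of modest and unknown size. Protocol 6.4, supported by 7.2 and 7.2.1, permits removal from the study for poor diary or dose compliance alone. Only one optional visit follows, and for removals well before Week 16 the obtainable EASI and vIGA are replaced by placebo-based imputation. This sits badly with a treatment-policy estimand.

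It is tempting to conclude that the effect is biased toward zero. The documents do not establish this. Shrinkage requires that the removed active-arm subjects were benefiting. If they became non-compliant because they were not benefiting, the bias is near zero or may reverse. The shrinkage of about 5% rests on three assumptions: 5% of an active arm removed, average true benefit in those subjects, and no benefit retained by the imputation. The power figures add the assumption that these removals come on top of the planned 10%, and the conclusion does not depend on them. The case for change is that the missing data are avoidable and cheap to avoid.

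**What to change.** By protocol amendment:

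- **6.4:** state that missed diary entries or missed doses alone are not grounds for withdrawal from the study. Such subjects are counselled and asked to continue all scheduled efficacy assessments through Week 16 and follow-up.
- **7.2 and 7.2.1:** align the non-compliance and protocol-violation grounds with this and with the estimand in 9.4.2, so that the same removal cannot occur by another route. Check the wording on withdrawal after an important deviation in Appendix 2 for the same reason.
- **Unchanged:** safety and subject-interest grounds, voluntary withdrawal, the handling of over-dosing (which 6.4 also classes as non-compliance), and every decision about study drug.
- **SAP IV.H.3:** continue to handle treatment non-compliance through the per-protocol set; add diary non-compliance to the list if wanted.

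The cost is an amendment with the approvals described in Appendix 2, plus some additional attended visits by poorly compliant subjects. All of these visits are already in the schedule.
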